HD-sEMG was recorded and processed using a Dell laptop (Latitude 5500, Dell Canada, Toronto, ON, Canada). HD-sEMG signals were recorded in monopolar and converted to digital using a 16-bit multichannel amplifier (Quattrocento, 400-channel EMG amplifier, OT Biolettronica, Torino, Italy; Common Mode Rejection Ratio > 95 dB). Signals were amplified (150V/V), sampled at 2048 Hz and bandpass filtered (10–500 Hz; -3 dB bandwidth). Data were further filtered using a 30 Hz highpass filter (2nd order Butterworth) to minimize electrocardiographic noise (Drake and Callaghan 2006). Single differential spatial filtering of adjacent monopolar signals within each row were calculated using OT Biolab + (OT Biolettronica, Torino, Italy), resulting in three differential values for each row of the grid. Root mean square (RMS) was then calculated for each differential signal and averaged within rows to determine individual row RMS (e.g. row 1 RMS). Shifts in the distribution of EMG amplitude within the LT were considered to be indicated by statistically significant differences in row RMS between conditions. Whole-muscle LT RMS was calculated by averaging RMS across all 8 rows. Data were exported from OT BioLab+ (version 1.3.2, OT Biolettronica, Torino, Italy) as a .csv file in 0.1 second epochs. RMS for each contraction was defined as the maximum RMS value achieved over a 1.5 second interval within each arm elevation repetition. The data from the 1st and 10th repetition were removed and mean of RMS EMG values from 2nd through 9th repetitions was calculated for statistical analysis.

Statistical Analysis

Inferential statistical analysis was performed using SPSS (Version 25; IBM Corp, Armonk, New York, USA). A two-way repeated measures ANOVA was used to determine if differences in whole-muscle LT excitation existed between taping and loading

conditions. One-way repeated measures ANOVAs were also conducted to determine the effect of tape condition during the loaded condition on the spatial distribution of excitation for each row.

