Normality for all procedures was assessed by Shapiro-Wilk's test of normality. Data were considered normally distributed if $p > .05$. Sphericity was assessed by Mauchly's test of sphericity. The assumption of sphericity was met if $p \leq .05$. For the two-way repeated measures ANOVA, outliers were considered to be studentized residuals greater than ± 3 standard deviations. For the one-way repeated measures ANOVAs, outliers were determined by boxplot inspection, with values greater than 1.5 box-lengths from the box considered outliers. Alpha was set at $p \leq .05$ for all statistical tests. A small effect size is considered $n^2 = 0.01$, a medium effect size is considered $n^2 = 0.06$, and a large is considered $n^2 = 0.14$ (Cohen 1988).

RESULTS

For comparison of whole-muscle LT excitation, analysis of studentized residuals indicated that the data were normally distributed, as assessed by Shapiro-Wilk's test of normality ($p > .05$). No outliers were present. One participant was removed from the analysis due to technical error. Another was removed due to incomplete data, resulting in $N = 20$ participants for the two-way ANOVA, and $N = 21$ for the one-way ANOVAs. Mauchly's test of sphericity was not met, $X^2(2) = 7.329, p = .026$. As such, a Greenhouse-Geisser correction was applied. There was no statistically significant interaction between tape and loading condition, $F(1.499, 28.476) = 1.368, p = .266$ (Figure 3). There was, however, a main effect for the loaded condition on whole-muscle LT excitation with a very large effect size, $F(1, 19) = 38.038, p < .001$, partial $\eta^2 = .667$. Across all tape conditions,

whole-muscle LT RMS in the loaded condition ($M = .055$ V, $SE = .005$) was significantly higher than the no-load condition ($M = .038$ V, $SE = .004$), with a mean difference of .017 V (95% CI, .011 to .023). There was no main effect of tape condition on whole-muscle LT RMS, $F(1.967, 37.38) = 0.370, p = .690$.

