For comparison of spatial distribution of excitation, data for row one baseline, row five baseline, row five sham, and row six KT were not normally distributed as assessed by Shapiro-Wilk test of normality ($p < .05$). Mauchly's test of sphericity was not met $p < .05$ in row one in the loaded E-KT condition, as such, a Greenhouse-Geisser correction was applied. Row one contained four outliers (load; N-KT, E-KT and S-KT) and row eight contained three outliers (load; E-KT and S-KT) as assessed by boxplot inspection. Statistical analysis was conducted with and without the inclusion of outliers, and it was determined that the outliers did not affect the results. As such, outliers were not removed from analyses. There were no significant differences across tape conditions in grid row RMS (Table 1).

Achieved power for the whole muscle excitation load main effect was estimated post-hoc using G*Power (3.1.9.3, Faul, Erdfelder, Lang, & Buchner, 2007). Given an analyzed sample of $N = 20$, with $\alpha = 0.05$ and an effect size of 0.667 (partial η^2), the achieved power ($1 - \beta$ - error probability) is > 0.99 .

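### The row-by-row ANOVAs compare amplitude within each row; no analysis tests whether the distribution of excitation across rows differs by tape

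*Combined protocol and SAP*

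**What the plan says.** Data processing and extraction defines row RMS as the average of the differential signals in a row, on the absolute scale, and gives the rule for reading it: "Shifts in the distribution of EMG amplitude within the LT were considered to be indicated by statistically significant differences in row RMS between conditions". The same section says "Whole-muscle LT RMS was calculated by averaging RMS across all 8 rows".

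Statistical Analysis names two kinds of model. One is a two-way ANOVA of tape and load on whole-muscle RMS. The other is the row analysis: "One-way repeated measures ANOVAs were also conducted to determine the effect of tape condition during the loaded condition on the spatial distribution" of excitation, row by row. It adds "Alpha was set at $p \leq .05$ for all statistical tests" and gives no multiplicity adjustment. It does not say how many significant rows would count as a shift.

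RESULTS gives the analysis sets, "resulting in $N = 20$ participants for the two-way ANOVA, and $N = 21$ for the one-way ANOVAs". It opens the row findings with "For comparison of spatial distribution of excitation, data for row one baseline, row five baseline, row five sham, and row six KT" and concludes "There were no significant differences across tape conditions in grid row RMS (Table 1"). Row as a factor, a tape by row term, a normalised row profile and a centroid are not described anywhere.

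**The concern.** Distribution is a relative property: how excitation is shared among rows. A test of one row's absolute RMS cannot tell a change in that row relative to the others from a change common to all rows. Listing which rows reach significance does not compare rows with each other either.

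The rule can therefore fail both ways. A uniform proportional change can be called a shift, and small opposite changes in different rows can go undetected. The whole-muscle test does not fill the gap, because opposite changes cancel in the eight-row mean. At stake is what the null row results support. They are the only evidence offered on spatial distribution, and they do not test it.

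**Working it through.** **Figures to reproduce.** The text gives no figure for the spatial analysis. Its one power figure (> 0.99, load main effect) does reproduce: λ = 0.667/0.333 × 20 = 40.06 on F(1, 19) gives 0.99997. It has no bearing on the row tests.

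**Structure.** Write log RMS for participant i, tape t and row r as

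y = aᵢ + bᵣ + cₜ + dₜᵣ + error,

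with cₜ a tape effect common to all rows and dₜᵣ the departure of row r from it. A shift in distribution means dₜᵣ ≠ 0. The row ANOVA tests whether cₜ + dₜᵣ is equal across tapes.

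- If c ≠ 0 and d = 0, the null hypothesis is false in every row although nothing has shifted.
- If c = 0 and d ≠ 0, each row test carries the error shared by all rows, which a tape by row contrast removes.
- The whole-muscle mean cannot help in the second case. With equal row amplitudes, +3% in four rows and -3% in four gives (4 × 1.03 + 4 × 0.97)/8 = 1.00.

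None of this depends on simulation.

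**Illustrative size.** From the document: N = 21, 3 tapes, 8 rows, p ≤ .05 per test. Assumed, because the available text gives no row-level values: normal log-RMS errors; within-participant SD 0.10 or 0.20; equal between-row error correlation ρ of 0, 0.5 or 0.8; one of three tapes differing. The whole-muscle row of the table is a loaded-only, N = 21 stand-in for the actual two-way model. T×R is the tape by row F test with Greenhouse-Geisser (GG) correction. There were 10,000 runs per cell; entries are proportions significant at ρ = 0 / 0.5 / 0.8.

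| Scenario and test | SD 0.10 | SD 0.20 |
|---|---|---|
| No effect: ≥1 row | .341 / .264 / .163 | .340 / .258 / .165 |
| No effect: ≥2 rows | .058 / .085 / .085 | .059 / .087 / .088 |
| No effect: T×R | .016 / .018 / .019 | .016 / .020 / .019 |
| Uniform -5%: ≥1 row | .971 / .806 / .632 | .639 / .452 / .305 |
| Uniform -5%: ≥2 rows | .842 / .641 / .522 | .249 / .238 / .204 |
| Uniform -5%: whole muscle | .999 / .585 / .422 | .641 / .178 / .134 |
| Uniform -5%: ≥1 row, whole muscle null | .001 / .223 / .210 | .155 / .276 / .170 |
| Uniform -5%: T×R | .020 / .020 / .019 | .016 / .019 / .019 |
| ±3% redistribution: ≥1 row | .722 / .650 / .512 | .446 / .370 / .267 |
| ±3% redistribution: ≥2 rows | .334 / .331 / .326 | .105 / .128 / .142 |
| ±3% redistribution: T×R | .302 / .706 / .997 | .054 / .115 / .408 |
| One row -6%: T×R | .106 / .273 / .802 | .031 / .055 / .143 |

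Check: eight independent tests give 1 - 0.95⁸ = 0.337, against .341 simulated.

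The rules run at different error rates, so the redistribution lines are not a like-for-like power comparison. If correlation instead decays with distance between rows (0.8 or 0.95 between neighbours), T×R rejects under a uniform 5% drop in .035 to .043 of runs. The uncorrected F rejects in .105 to .129, which is why the correction is needed.

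**Scale.** In a further simulation with a uniform 15% fall, T×R on raw RMS rejected in 62% to 97% of runs, and on log RMS in about 5% (uncorrected). The analysis therefore has to be on a relative scale.

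**Precision available.** For one row's tape ratio relative to the row mean, the 95% CI half-width is

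exp(t₂₀ × SD × √[2(1 - ρ)(7/8)/21]) - 1, with t₂₀ = 2.086.

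At SD 0.10 and ρ = 0: exp(2.086 × 0.10 × 0.2887) - 1 = 6.2%. At ρ = 0.5 and 0.8 it is 4.3% and 2.7%. At SD 0.20 the three values are 12.8%, 8.9% and 5.5%.

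**The case against.** The strongest reply is that little follows in practice. The rule is declared openly, the tests are described as being for each row, and the concluding sentence in RESULTS speaks only of row RMS. No row was significant, so a uniform change was not mistaken for a shift, and the text does not claim that the distribution was unchanged. If every row's true mean were equal between tapes, there could be no shift. On this view a wording correction is enough.

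Much of that stands. Of the two failures, only a missed redistribution bears on the reported result. But non-significance in each row does not establish equality, and the results are still headed as a comparison of spatial distribution.

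Other fair points:

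- The simulated rates rest on assumed values, and T×R power for the ±3% case runs from 5% to over 99%. That gives no usable estimate for this trial.
- Table 1 and Figure 3 were not in the text available for this review. Table 1 may already hold some row-level summaries.
- The T×R test separates a shift from a uniform change only when the change is proportional, and a null result at low power settles nothing.
- For a shift confined to one row it can be the weaker test: at SD 0.10 and ρ = 0, Bonferroni-adjusted row tests find about 24%, against 11%.
- RESULTS reports non-normal data in some rows and outliers in rows one and eight, which the simulation ignores.

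These limit the weight of the numbers and the hopes for the added test. They do not make row-wise amplitude tests into a test of distribution.

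**Conclusion.** The point holds and should be fixed. The decision rule is wrong for the question it is meant to answer, and no analysis in the document answers that question. This follows from the model structure alone.

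The size is illustrative. Under the stated assumptions, at least one row is significant after a uniform 5% drop in 31% to 97% of runs. The GG-corrected tape by row test rejects in about 2% with equal correlation and about 4% with distance decay. A ±3% redistribution is missed by the one-row rule in 28% to 73% of runs, and by a two-row rule in 67% to 90%.

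The consequence is limited to interpretation. The null row results do not show whether tape altered the spatial pattern. The whole-muscle findings are untouched.

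**What to change.** 1. **Relabel.** Keep the decision rule as a record of what was done, but describe the row ANOVAs in Statistical Analysis and RESULTS as row-wise amplitude comparisons. Suggested RESULTS text: *Row-wise RMS amplitude did not differ significantly between tapes (Table 1); these comparisons do not test whether the distribution across rows differed.* This step alone makes the text correct.
2. **Add one analysis if anything is to be said about distribution.** Fit a tape by row repeated-measures ANOVA of log(row RMS), loaded condition, N = 21, GG-corrected. State that it was added post hoc after the row results were known, and report it whatever it shows. Speak of a shift only if the interaction is significant. Follow up with Holm-adjusted tests on each row's log RMS minus the participant's mean log RMS across rows in that condition. Run it with and without outliers, as was done for the row tests.
3. **Report precision.** Give tape ratios per row with 95% CIs, the observed SD and the between-row correlation, so readers can see what size of shift the data exclude.

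The cost is one re-analysis of data already exported, plus wording. The drawbacks are that effects become ratios rather than volts, the analysis is post hoc, and the corrected test is conservative. Power is low if row errors are weakly correlated, the SD is large or the shift lies in one row, so the result may be inconclusive.

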Acute Effect of Inhibitory Kinesio-tape of the Upper Trapezius on Lower Trapezius Muscle Excitation in Healthy Shoulders

NCT04711447

March 14th, 2023

METHODS

Design

A repeated-measures, crossover design was used to determine the acute effect of KT applied to the UT on muscle excitation of the LT. Participants were asked to perform a repeated arm elevation task during three different taping conditions: no KT, experimental KT and sham KT. During each taping condition, participants performed a bilateral repeated arm elevation task during two loading conditions: no load and loaded with 2.3 kilograms. All six conditions were tested during one visit, with the no load condition preceding the loaded condition for each taping condition. A baseline trial (no KT; N-KT) was performed first, followed by both an experimental-KT (E-KT) and sham-KT (S-KT) condition. The order of the E-KT and S-KT conditions were randomized and counterbalanced (Research Randomizer v4.0, Social Psychology Network, Lancaster, PA, United States) (Figure 1). Testing for each tape condition during both the no load and loaded conditions lasted approximately 10-minutes, requiring a total of 45-minutes of testing time per participant including screening, EMG set-up and clean-up. No wash-out period was given between S-KT and E-KT taping conditions; the first tape condition was removed upon completion of the arm elevation task and the second tape condition was applied immediately after. KT was applied to the UT and muscle excitation (EMG amplitude) was measured in the LT using the same 32-electrode high-density surface electromyography (HD-sEMG) grid during the repeated arm elevation task. All data were collected in a laboratory setting at the University of Manitoba.

Participants

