For each tape and load condition participants performed ten repetitions of standing bilateral arm abduction in the frontal plane beginning with their arm resting by their side (Figure 2C). Participants were instructed to raise their arms bilaterally to full shoulder abduction (180°) while keeping their elbow fully extended and forearm supinated (Figure 2D). Participants were familiarized with performing the arm elevation task immediately prior to performing the N-KT condition (Figure 1). A research assistant performed the arm elevation task at a rate of 40 beats per minute while participants were asked to follow a metronome and mimic the researcher. Each repetition lasted for a total of three beats, or ~3 seconds, beginning with their arms by their sides. The participant's arm ascended into abduction where the first beat occurred at maximal abduction, followed by descending back to starting position where the second beat occurred. The third beat acted as a rest beat before beginning the next repetition and continued this for a total of 10 repetitions. An external load of 2.3kg was utilized to increase muscular demand while still allowing the participant to perform the required volume of arm abductions. Clinically, a load of 2.3kg is used to exacerbate scapular dyskinesia when present (McClure et al 2009).

Data processing and extraction

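### The tape F test counts the always-first, unrandomised no-tape trial as a tape level; the randomised E-KT minus S-KT contrast has no specified estimate, CI or period adjustment

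*Combined protocol and SAP*

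**What the plan says.** METHODS, Design, fixes the order of the three taping conditions: "A baseline trial (no KT; N-KT) was performed first, followed by both an experimental-KT (E-KT) and sham-KT (S-KT) condition". Randomisation covers only the last two: "The order of the E-KT and S-KT conditions were randomized and counterbalanced". The same section adds: "No wash-out period was given between S-KT and E-KT taping conditions". The task section says: "Participants were familiarized with performing the arm elevation task immediately prior to performing the N-KT condition". Each tape-by-load condition has ten repetitions, and the unloaded set precedes the loaded set.

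Statistical Analysis names two procedures. For the whole muscle: "A two-way repeated measures ANOVA was used to determine if differences in whole-muscle LT excitation existed between taping and loading" conditions. For the grid rows: "One-way repeated measures ANOVAs were also conducted to determine the effect of tape condition during the loaded condition". It mentions no period, sequence or carry-over term and no pairwise tape contrast.

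RESULTS concludes for the whole muscle: "There was no main effect of tape condition on whole-muscle LT RMS", with F(1.967, 37.38) = 0.370, p = .690. For the rows it says: "There were no significant differences across tape conditions in grid row RMS". The only confidence interval in the text, and the only power figure, concern load.

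**The concern.** N-KT directly follows familiarisation. The first tape block comes after 20 task elevations and the second after 40, half of them loaded. Any difference between N-KT and a taped condition therefore mixes tape with learning, fatigue and change at the electrode-skin interface. The three-level F test pools that confounded comparison with the single randomised one.

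A null result from this test has two readings as regards tape versus no tape: no effect and no drift, or an effect of taping offset by drift. The question that the randomisation can answer, inhibitory tape against sham, has no stated estimate or interval. The reader cannot see which effects the null excludes.

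**Working it through.** **Inputs.** N = 20 in the two-way ANOVA; tape F(1.967, 37.38) = 0.370, p = .690; interaction F(1.499, 28.476) = 1.368; load F(1, 19) = 38.038 with mean difference 0.017 V; loaded and unloaded means 0.055 V and 0.038 V (all RESULTS). The documents give no drift size, no E-KT or S-KT means in the visible text, and no SD of their difference.

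**1. Reproduce the reported test.** The upper tail of F(1.967, 37.38) at 0.370 is 0.690, as stated.

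**2. Identify the model.** The numerator df of 1.967 is 2 × 0.9835, that is, two df times the Greenhouse-Geisser epsilon, so tape has three levels including N-KT. The ratios of error to numerator df are 37.38/1.967 = 19.00 and 28.476/1.499 = 19.00, which is N − 1. A sequence factor would give 18. No period or sequence term was fitted.

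**3. What the reported F allows.** With r the ratio of the smaller to the larger contrast variance, epsilon = (1 + r)²/[2(1 + r²)]. Setting this to 0.9835 gives r = 0.771. The largest possible contrast has t² = F(1 + r)/r = 0.370 × 1.771/0.771 = 0.850, so |t| ≤ 0.92 and p ≥ .37 on 19 df. Removing a share q of the E-KT minus S-KT variance as period changes t² to t² × (18/19)/(1 − q). Reaching the 18-df critical value of 2.101 needs q = 1 − 0.850 × (18/19)/2.101² = 0.82.

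**4. Size of the confounding (assumed drift).** Let the residual SD be 1, the sequences 10:10, the drift δ per block, and the true tape effect zero. On average a tape block lies 1.5 blocks after N-KT, so E-KT minus N-KT shifts by 1.5δ. E-KT minus S-KT shifts by −δ in one sequence and +δ in the other, which averages to zero. The F columns are from simulation.

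| δ (SD per block) | E-KT − N-KT | E-KT − S-KT | F significant | F ≤ 0.37 |
|---|---|---|---|---|
| 0 | 0 | 0 | 5% | 31% |
| 0.1 | 0.15 | 0 | 7% | 27% |
| 0.25 | 0.38 | 0 | 19% | 14–15% |
| 0.5 | 0.75 | 0 | 62% | 1.5% |

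A drift of 0.5 SD therefore fits the reported F only if taping had an opposite effect.

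**5. Effect of omitting period on E-KT minus S-KT (same assumptions).**
- Type I error, unadjusted: about 4.6%, 3.8% and 1.7% at δ = 0.25, 0.5 and 1.0. Period-adjusted, it stays at about 5%.
- Power for a 0.9 SD effect, unadjusted against adjusted: 77% and 77% at δ = 0; 73% and 77% at 0.5; about 60% and 77% at 1.0.
- With sequences of 11:9, unadjusted bias is (11 − 9)/20 × δ, that is 0.05 SD at δ = 0.5 and 0.10 SD at δ = 1.0. The adjusted estimate is unbiased.

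**6. Carry-over.** If half of a −0.9 SD E-KT effect persisted into a following S-KT block, either estimate becomes −0.9 + 0.45/2 = −0.675 SD. A period term does not repair this.

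**7. Width of the missing interval (assumed SD of the E-KT minus S-KT difference).** The half-width is 2.101 × SD/√20. SDs of 0.003, 0.006, 0.0123 and 0.018 V give 0.0014, 0.0028, 0.0058 and 0.0085 V. The third SD is that of the load difference, 0.017/√38.038 × √20, used only as a reference. Against the mean over loads, (0.055 + 0.038)/2 = 0.0465 V, the range is about 3% to 18%.

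**The case against.** The strongest reply is that the period part gains little. Adjustment helps noticeably only at drifts of 0.5 SD or more, which the reported F makes improbable unless taping opposed the drift. At zero drift it costs a trace of power. Counterbalancing already removes additive period bias, and the unadjusted test is conservative. If allocation was 11:11, losing two participants at random leaves 10:10 in 121/231 = 52% of cases and 11:9 at worst. This stands: period adjustment is a refinement and does not carry the point.

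Drift also moves E-KT and S-KT equally on average. Offsetting could therefore hide only an effect common to both tapes, not a large load-averaged difference between E-KT and sham. That is correct, and it limits the masking argument to tape versus no tape.

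The design has safeguards: familiarisation, a grid left in place all visit, and discarded first and last repetitions. They reduce some sources of drift but do not exclude fatigue or signal change, and they do not randomise N-KT.

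Table 1 and Figure 3 are not shown and may contain condition means or intervals, so absence can be asserted only for the visible text and the plan. The df check covers the two-way ANOVA alone, because no row-level df are visible. No discussion text shows that the null was in fact read as tape versus no tape.

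**Conclusion.** The concern holds. That N-KT is a non-randomised, always-first tape level, and that the two-way model has no period or sequence term, follows from the documents and their own degrees of freedom. The plan specifies no E-KT minus S-KT estimate with a CI.

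The consequence is for interpretation, not for a hidden positive: the bound of |t| ≤ 0.92 makes a significant load-averaged whole-muscle difference between E-KT and sham unlikely even after adjustment. That bound does not extend to the loaded-only row tests or to the loads taken separately. The sizes quoted for drift, bias, power and interval width rest on assumed drifts and SDs. Counts per sequence after exclusions are not given, and the 21 participants in the row analyses cannot split evenly. Unequal carry-over remains possible with no wash-out. The change should be made, though the reported whole-muscle null is likely to stay non-significant.

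**What to change.** Make E-KT minus S-KT the main tape estimate and analyse it as a two-period, two-sequence crossover. Take each participant's difference, averaged over load and also separately by load. Average it within each sequence, and use the mean of the two sequence means (18 df at N = 20). Report it with a 95% CI and the number analysed per sequence, and do the same for each row.

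A mixed model with tape, load, their interaction and period is an alternative if it includes participant, participant-by-tape and participant-by-load random effects. With a random intercept alone, simulated type I error for E-KT minus S-KT was 14.6% when the participant-by-tape SD was 1, and 1.3% when only a participant-by-load SD of 1 was present.

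Present N-KT comparisons as descriptive and unrandomised, and reword the null statements on tape to match. State carry-over as a limitation. A first-tape-only comparison may be added, but two sequences cannot cleanly isolate carry-over. Its CI is √[2(1 + b²)] times as wide, where b is the between-person SD in residual SDs: 1.6, 2.0 or 3.2 times for b = 0.5, 1 or 2. Using N-KT as a baseline covariate reduces this to about 1.5, 1.7 or 1.9.

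The cost is a re-analysis with each participant's recorded tape order, one degree of freedom, and the loss of inferential status for N-KT comparisons. No new data are needed.

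### The tape result, which is the study question, is reported only as an absent main effect from a three-condition F, with no experimental-minus-sham estimate or interval in the running text

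*Combined protocol and SAP*

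**What the plan says.** METHODS, Design sets the purpose of the study: to "determine the acute effect of KT applied to the UT on muscle excitation of the LT". Of the three tape conditions, only two had their sequence randomised: "The order of the E-KT and S-KT conditions were randomized and counterbalanced". The third did not: "A baseline trial (no KT; N-KT) was performed first". The same section says that there was no wash-out between the two taped conditions.

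In RESULTS the whole-muscle tape finding is one sentence: "There was no main effect of tape condition on whole-muscle LT RMS, $F(1.967, 37.38) = 0.370, p = .690". Load, the second factor, is reported more fully: condition means with standard errors, partial eta-squared .667, and a marginal comparison ("Across all tape conditions") "with a mean difference of .017 V (95% CI, .011 to .023").

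The section ends with the document's only power statement: "Achieved power for the whole muscle excitation load main effect was estimated post-hoc using G*Power". It uses N = 20, alpha 0.05 and the observed partial eta-squared of .667, and gives power above 0.99.

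**The concern.** The factor that the study was designed to examine is reported with less information than the factor that was not its main question.

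- **Wording.** The tape sentence states absence, but the evidence is a non-significant test. A reader cannot tell from the text how large a tape effect the data leave open.
- **Comparison tested.** The F has two numerator degrees of freedom before correction and covers all three conditions. Any contrast with N-KT is confounded with test order, because N-KT was always first. E-KT versus S-KT is the only order-randomised, sham-controlled contrast, and the running text does not estimate it.
- **Power.** The one figure given concerns load and is computed from load's own observed, already significant effect. It adds nothing to p < .001 and carries no information on tape.

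At stake is whether a reader can separate a tape effect shown to be small from one that was simply not detected.

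**Working it through.** **Reproducing the document's figures.**
- Load: partial eta-squared = 38.038/(38.038 + 19) = .667, as stated. The standard error of the difference is .017/√38.038 = .00276. With t(.975, 19) = 2.093 the interval is .017 ± .0058, or .0112 to .0228, matching .011 to .023.
- Load power: f² = .667/.333 = 2.003. The noncentral F on 1 and 19 df gives .9999 whether the noncentrality is f² × 20 or f² × 19. The stated figure is right.
- Tape: F = 0.370 on 1.967 and 37.38 df gives p = .690, as stated. The implied partial eta-squared, not given in the running text, is (0.370 × 1.967)/(0.370 × 1.967 + 37.38) = .7278/38.108 = .019.

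**E-KT minus S-KT in SD units (no outside assumption beyond pooled error).**
- Half-width: t(.975, 38)/√20 = 2.024/4.472 = 0.453 SD of the paired difference. This follows from N and df alone.
- Centre: the sum of squares for any pairwise contrast cannot exceed the tape sum of squares, so t² ≤ 2F = 0.740 and |t| ≤ 0.860. The observed difference is then at most 0.860/4.472 = 0.192 SD.
- The limit further from zero therefore lies between 0.453 SD (observed difference zero) and 0.453 + 0.192 = 0.645 SD.
- Pooling the error is reasonable: the implied sphericity epsilon is 1.967/2 = .98. With a contrast-specific error on 19 df the half-width is 2.093/4.472 = 0.468 SD.

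**In volts.** This needs the correlation between tape conditions, which the text does not give. ASSUMPTION: it equals the correlation between load conditions.
- Load correlation from the reported SEs (.005 and .004): r = (.005² + .004² − .002756²)/(2 × .005 × .004) = .835.
- SD of participants' overall means: √[20 × (.005² + .004² + 2 × .835 × .005 × .004)/4] = .0193 V.
- SD of the paired tape difference: √[6 × .0193² × (1 − ρ)/(1 + 2ρ)].

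| ρ | SD of difference (V) | Half-width (V) | Largest further limit (V) |
|---|---|---|---|
| .5 | .0236 | .0107 | .0152 |
| .835 | .0117 | .0053 | .0076 |
| .95 | .0062 | .0028 | .0040 |

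The half-width is also the smallest possible further limit, so over ρ = .5 to .95 that limit runs from about .003 to .015 V.

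The correlation is itself derived from rounded figures, so the rounding of both SEs and of the difference has to be carried through together. The load correlation then ranges from .78 to .92, the half-width from .0037 to .0059 V, and the further limit from .0037 to .0083 V. Rounded, the further limit is .004 to .008 V. Against the load effect this is .004/.017 = 24% to .008/.017 = 47%.

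**The case against.** - **The power figure is not an error.** This stands. It is correct and explicitly labelled as load. A reader might infer that above 0.99 is offered as reassurance about the null tape result, but nothing in the document applies it to tape. The remaining complaint is redundancy.
- **The tape sentence is ANOVA shorthand.** Largely fair. F and p follow at once, and the interaction and grid-row results nearby are worded in terms of statistical significance. A reader might infer a claim that tape is ineffective or equivalent to sham; the supplied text has no discussion and makes no such claim. The careful wording used elsewhere does, however, make the edit easy to justify.
- **E-KT versus S-KT was never named as primary.** True. The Statistical Analysis section sets out a three-condition ANOVA and the document reports it, so this is not an omitted planned analysis. The case for the contrast comes from the design: it is the only comparison with randomised order.
- **Figure 3 or Table 1 may hold more.** Possible, since neither is shown, so the point is limited to the running text. Cell means alone would not supply an interval for a paired difference.
- **The contrast has its own weakness.** This stands. There was no wash-out, and RESULTS reports two of 22 participants removed from the two-way analysis, so order balance among the 20 is unknown. An interval that ignores order could be biased or too narrow.
- **The volt figures rest on an assumption.** They do. Nothing in the document ties the between-tape correlation to the between-load correlation, so they only illustrate size.

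**Conclusion.** The point holds as a reporting fault that should be fixed. The running text states no tape effect on the strength of a non-significant three-condition F, and it gives no estimate or interval for the one order-randomised comparison.

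The firm result is in SD units: a half-width of about 0.45 SD of the paired difference, with the further limit between 0.45 and 0.65 SD, given N = 20 and pooled error. The volt range of .004 to .008 is conditional on the borrowed correlation. Both calculations also leave out any period or carry-over effect.

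No reported test, p-value or N is shown to be wrong. The figures do not show that tape has an effect or that a real one was missed. They show only that differences of this size are not ruled out and that the text does not say so.

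**What to change.** 1. Report the E-KT minus S-KT mean difference in whole-muscle RMS, in V with a 95% CI, averaged over load to match the marginal form of the load result. Take it from a paired analysis that includes a period (tape order) term. State how many of the 20 analysed participants had each order, and note that without a wash-out carry-over cannot be excluded.
2. Reword the tape sentence, for example: *No statistically significant main effect of tape condition was detected, F(1.967, 37.38) = 0.370, p = .690, partial eta-squared = .019; E-KT minus S-KT, averaged over load, was [x] V (95% CI [a] to [b]), and differences within this interval are not excluded.*
3. Optionally, delete the post-hoc load power paragraph. A post-hoc power for tape should not replace it, since that would only restate p = .690.

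The cost is one added contrast from data in hand and a few lines of text. The existing tests and p-values stay as they are. The precision statement will look less favourable than a power above 0.99.
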